Administration of Morphine (.08 mg/kg). As described, individuals with respiratory (e.g., asthma), hepatic, renal, cardiac, or other medical conditions that would contraindicate morphine administration will be excluded. Blood tests verifying liver and kidney function will be conducted and reviewed by one of the study physicians ([name], [name] or [name]) prior to implementing the procedure. Subjects with a history of allergic reaction to opioids or anesthesia are excluded. We are also excluding individuals with alcohol and substance abuse disorders because opioids have significant abuse potential. An appropriately licensed CRU pharmacist will prepare the morphine doses onsite. A registered nurse will administer the drug as prescribed by [name], [name], or [name]. For safety reasons, the registered nurse will be aware that the syringe could contain either saline or morphine. The subject will remain in a recumbent position during the procedure to prevent falls. Drs. [name], [name], or [name] will be available by pager to provide any medical oversight as needed. A nurse will monitor heart rate, blood pressure, SPO₂, and respiration rate during the procedures. The CRU maintains an anaplylaxis treatment kit and a supplemental oxygen tank. Sufficient naloxone will be available onhand. An Ambu, CPR bag is also available to facilitate mechanical ventilation if needed. The CRC also has an AED. The protocol will include a standing naloxone order signed by [name], [name], or [name] sufficient to fully reverse the adverse effects of morphine should a subject experience respiratory distress or other morphine-related complications. Nurses will be trained under the direction of Drs. [name] and [name]. The CRC has established a standard emergency protocol to ensure the safety of subjects undergoing opioid administration. We are using a routine dose of morphine based on body weight that is typically lower than is commonly use in emergency departments to treat acute musculoskeletal pain(139). This substantially minimizes possibility of toxicity and reduces potential side effects. Drs. [name] and [name] are both very experienced physicians who specialize in and

routinely care for patients with opioid dependence. They have considerable expertise with clinical and research protocols involving opioid administration and naloxone/naltrexone blockade. [name] is also very experienced in these domains and will be available as study physician in the event that both Drs. [name] and [name] are unavailable. Subjects receiving morphine under sleep deprivation conditions will be required to remain on the Unit for a recovery period (overnight) prior to discharge to prevent accidents due to impairment caused by morphine plus sleep deprivation. After the undisturbed sleep condition, subjects will return home the same day, but will not be permitted to drive and instructed not to engage in potentially hazardous activities for the next 12 hours, e.g., cooking, driving, operating heavy machinery, or drinking alcohol or other depressants.

The nursing staff is well trained to assist subjects experiencing side effects such as nausea and emesis. As described, food and drink is limited and restricted prior to injection to minimize these side effects. Subjects will complete the 6-item drug effect VAS and an adjective checklist (36 items), after injection to gather data on frequency and severity of side effects. [name] has used these measures in his opioid pharmacology work to study side-effects of opioid medications. This will be reported regularly to the IRB and our data safety and monitoring committee for review. These measures were specifically designed to capture common and uncommon side effects of morphine and opioid medications.

Sleep Disruption/Deprivation: Because sleep deprivation lowers seizure threshold and may trigger manic episodes in individuals with bipolar disorder, individuals with these conditions are excluded as described. All subjects undergoing sleep deprivation will remain under surveillance on the medical research unit for a recovery night sleep to prevent accidents that might be caused by drowsiness. Because sleep deprivation is a stressor that can impact mood, we have excluded subjects with major psychopathology or acute psychological distress.

Topical Capsaicin: Prior to capsaicin application, we will ensure that the skin is not compromised at the site of administration. Participants are instructed that they may discontinue any of the pain procedures at any time should they become too intense or unpleasant. Ice will be available for application, which dramatically reverses the heat-capsaicin pain if subjects wish to discontinue. Further, when the protocol is finished, we will cover the application area with a large band-aid and give participants several additional band aids so they can keep the area covered in order to avoid accidentally rubbing it on any other bodily areas that could be potentially painful (e.g., rubbing their eye(s), mucous membranes).

Heat-Pain Testing: All pain testing equipment will be tested prior to use to ensure it is functioning properly. Johns Hopkins IRB requires that all devices are approved by bioengineers for safety and proper functioning before approval of any research protocol. Thermodes and devices touching participant's skin are sterilized before and after use with an appropriate agent. The thermal sensory analyzer has built-in safety features to prevent burning. The temperature to be used will not cause burn. For all of the standardized laboratory pain procedures, participants are repeatedly informed that they may terminate any of the procedures at any time, and participants are monitored continuously by the technician. In the event that a subject is injured in any way by any of the study procedures, [name], [name], or [name] will evaluate the condition and, if appropriate, refer the participant for medical attention and notify the IRB, as appropriate. Across hundreds of research participants with various conditions, we have had no adverse events deemed greater than mild (even this level AE occurs in < 1/100 cases) related to the use of these devices.

Cold Pain Pain Tolerance Task: There are no significant risks from immersion of a hand in cold water by a healthy individual for the 5 minute maximum time permitted. The task could exacerbate Reynaud's syndrome, therefore these patients are excluded.

Blood Samples. There is a very small chance that phlebotomy may cause hematoma, infection, anemia, and minor pain at the puncture site. However, these procedures are routinely performed without incident in medical settings, and catheters will be installed by qualified nursing staff according proper sterile technique.

Subcutaneous Injection: Subcutaneous injection is routinely performed without incident in medical settings. This route of administration was selected over intramuscular injection because it is better tolerated by patients (140). A qualified nursing professional will administer the subcutaneous injection according to proper techniques.

Saline Placebo: There are no risks associated with saline itself. Minimal risks associated with the routine IV catheterization procedure are described below. Catheters will be installed by qualified nursing staff.

Polysomnography testing. Very rarely, individuals may experience a mild allergic reaction to electrode gels/paste. The CRU has appropriate medicine (e.g., cortisone cream) to ameliorate discomfort as needed.

Physical Exam and Structure Diagnostic Interviewing. There are no known or reported medical risks associated with undergoing a physical exam or the proposed diagnostic interviews performed by a qualified professional.

Urine Sample. There are no risks to collecting a sample of urine. Strict confidentiality of the sample & results will be maintained.

Actigraphy. There are no risks associated with wearing a wrist actigraph.

Questionnaires. Minimal risks associated with completing the questionnaires and cognitive testing are subject fatigue and the possibility of minor psychological distress associated with answering sensitive questions regarding psychological functioning. Subjects are instructed that they do not need to disclose any information that may be too uncomfortable. A Certificate of Confidentiality has been obtained to further protect participant privacy and ameliorate subjects' concerns regarding sensitive information.

Emotion-Related Tasks: Participants will be made fully aware of the types of graphic content included in the International Affective Picture System images at the point of consent, and then again prior to engaging in the task. They will have opportunities to decline participation or discontinue participation at any time. Potential participants with severe or recurrent psychopathology will not be eligible to participate, so it is unlikely that participants will become severely distressed as a result of viewing these images.

Electromyography and Galvanic Skin Response Monitoring: Very rarely, individuals may experience a mild allergic reaction to electrode gels/paste. The CRU has appropriate medicine (e.g., cortisone cream) to ameliorate discomfort as needed.

Motivation, Reward-Related and Psychomotor Vigilance Tasks: To mitigate the unlikely potential for excessive fatigue and/or boredom, subjects will be reminded that they may discontinue any task at any time.

Additional Pain Testing: See risk minimization steps described above under Heat Pain Testing, Pressure Pain Threshold, and Cold Pain Tolerance Task.

Placebo Analgesia:

Risk 1: Infringement of participant autonomy. This risk is sensitively minimized when prospective subjects are given an “authorized deception” disclosure that alerts them to the use of deception in the research during the informed consent process. We inform research participants about the use of deception, the fact they have the opportunity to decline to participate, and that they will learn the specific nature of deception at the end of their study participation.

Risk 2: Distress and lack of trust in research. Revealing the truth about the study during the debriefing process may potentially result in participant’s distress who can be upset at learning how they were deceived. However, based on literature on deception in placebo research and our experience, no lack of trust in research have been observed.

Risk 3: Negative emotional reactions. No negative reactions or lasting negative consequences from learning the details regarding the use of deception have been observed. We believe this has been mitigated by the authorized deception part of informed consent.

From the perspective of researchers, the authorized deception may influence the placebo-induced analgesia by reducing beliefs and certainty about the treatment. This point deserves future research.

PET and MRI procedures: Before and during PET scans, the physiological and psychological status of each participant will be closely followed. Before and during each PET scan, blood pressure, heart rate, and rhythm strip will be carefully monitored.

A physician will monitor the physiological and psychological status of the participants before, during, and after inventions until the participant returns to the baseline level. The physician will institute the appropriate medical and psychological interventions when they are needed.

If an acute clinical problem is encountered in the course of the study, the participant will be referred for treatment as indicated.

c. Plan for reporting unanticipated problems or study deviations.

Any protocol deviations and/or adverse events will be systematically documented by [name], the PI, and reported immediately to the Johns Hopkins IRB. Case Report Forms (CRFs) will identify study participants by their initials and a unique study participant identifier. The participant’s name will not be attached to any data. CRFs will be stored in a locked office, which is only accessible to the study coordinator and authorized personnel. The principal investigator will provide an interim report of all adverse events to the IRB at the time of continuing review.

The FDA and IRB will be notified of serious adverse events associated with [¹¹C] raclopride, in accordance with the FDA and IRB reporting requirements.

All adverse events, unanticipated problems, or study deviations will be reported per the current JHM IRB guidelines pertaining to problem/event reporting posted on the JHM IRB website.

- d. Legal risks such as the risks that would be associated with breach of confidentiality.

Some of the personal health information gathered during the screening process or during treatment is sensitive. The laboratory blood testing will identify the presence of illegal drugs (if detectable), which might have consequences if they were released to others. Every effort will be made to maintain privacy and confidentiality. A number of procedures will be in place to prevent a breach of confidentiality. All potential subjects will be fully informed of their rights pertaining to disclosure of PHI in accordance with HIPAA regulations. The proposed research will be subject to the strict rules of confidentiality maintained at Johns Hopkins Medical Institutions. Confidentiality will be maintained by assigning participants a study number and numerically coding all data. One hard copy file linking the code number with identifying information will be kept in separate locked file with direct access available to the PI only. All records and research data will be kept in locked filing cabinets or computers. Information about urine toxicology screening results will be handled by [name] and the project coordinator and will be kept separately from the study clinical record in a locked file maintained by [name]. Only summaries of group data will be reported in any publications or presentations, with no identification of individuals. These precautions should serve to minimize legal risks to participants. The PI is a psychologist, licensed in the state of Maryland, and is bound by state laws on confidentiality. Further, Johns Hopkins is committed to protecting the rights of potential research participants. In light of this, the Hopkins IRB has developed a training program on protection of human subjects that is required for all Hopkins personnel engaged in research involving human subjects.

- e. Financial risks to the participants.

There are no financial risks or costs to study subjects for any of the procedures.

9. Benefits

- a. Description of the probable benefits for the participant and for society.

All participants will receive, at no cost, a comprehensive evaluation of their sleep and mental health status, including a screening polysomnographic sleep study, which might identify an occult sleep disorder such as sleep apnea. These individuals will be informed of any disorders identified and referred for appropriate clinical care. Other than mentioned above, there is no other benefit to participation for subjects in the study, but the risks to participation are minimal and justifiable.

10. Payment and Remuneration

- a. Detail compensation for participants including possible total compensation, proposed bonus, and any proposed reductions or penalties for not completing the protocol.

Subject Compensation

Visit 1	=	\$25
Visit 2	=	\$25
PSG Screen	=	\$75
US Condition	=	\$300

Date: 08/30/16 Principal Investigator: [name].

Application Number: NA_00071465

FA Condition	=	\$350
Completion Bonus	=	\$275
Total	=	\$1,050

Subjects will be remunerated up to \$1,050 for their effort (\$25 v1, \$25 v2, \$75 the PSG screen, \$300 for US Condition, \$350 for FA condition, and \$275 bonus). We have included a \$275 bonus to incent subjects to return and complete the second admission. For participants who leave the study early for any reason, they will receive partial compensation pro-rated as a function of their participation.

Optional Sleep, Pain, Emotions, and Reward Study Procedures

Participants who are eligible and elect to participate in the SPEAR study will be compensated an additional \$300 for daytime testing procedures: \$100 for each PET session, \$25 for each QST and reward testing session, and a \$50 completion bonus.

Thus, the total amount a participant could earn for participation if they are eligible and participate in all procedures associated with the Mechanisms of Sleep Disruption Hyperalgesia study and the SPEAR study is \$1,350. In addition to the participation payments, participants may earn a small amount of additional money (up to \$23.50) as part of the motivation tasks. This amount will not be advertised or included in screening or consenting because it could create expectancy effects that could bias results. However, participants will be informed that they can earn some additional money based on their performance on the tasks.

11. Costs

- a. Detail costs of study procedure(s) or drug (s) or substance(s) to participants and identify who will pay for them.

There are no costs to study participants.

Reference List

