Screening Visit 3 [inpatient Clinical Research Unit (CRU)]: Twenty-four hours prior to, and during admission for Visit 3 (v3) and all CRU visits, subjects will refrain from taking analgesics, hypnotics, and other centrally acting (e.g., caffeine) or anti-inflammatory agents. Subjects will undergo a standard PSG, as described below, to rule out occult sleep disorders and provide an adaptation night. Subjects meeting ICSD Criteria(78) for a sleep disorder (e.g. sleep apnea) will be ruled out and referred for clinical care.

Randomization Plan. Subjects passing v3 will remain on the unit and be randomized to receive either morphine or placebo during both of their US and FA admissions (v4 & v5). The Research Pharmacy will generate the randomization list to maintain double-blinding. We will use a dynamic probabilities algorithm with minimization(79, 80) to balance groups on sex, obesity (BMI), and age, since these factors influence pain and inflammation. We will also balance on Chinese ethnicity, due to its association with morphine metabolism(81). To control for sequence effects, we will counterbalance US and FA conditions by randomizing subjects to 1 of 4 sequences: 1) Placebo/US first; 2) Placebo/FA first; 3) Morphine/US first and 4) Morphine/FA first. Subjects randomized to FA first, will remain inpatient for 3 consecutive nights [(v4) FA1, FA2, Recovery]. After two weeks washout, they will complete their US admission(v5). Subjects randomized to the US sequences first will complete the US admission [(v4) US1, US2] followed two weeks later by their FA admission [(v5) FA1, FA2, & Recovery].

Experimental Assessments.

General Inpatient CRU Procedures. To maintain experimental control, subjects will not leave the unit during each admission (v3-5) and will not be permitted to sleep outside their prescribed nocturnal schedule. Staff will continuously monitor, maintain, and regularly document wakefulness. Subjects will wear actigraphs at all times during v3-5 to provide an additional, objective procedural integrity check. Standardized meals and snacks will be provided by the CRU. Breakfast will be served at approximately 7:30 AM. Subjects will continue to complete sleep and pain diaries during v3-5 to provide indices of spontaneous pain and fatigue.

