cocaine craving cues, video games, etc (Drobes and Tiffany, 1997; Wong et al, 2006). Thus, [¹¹C]raclopride provides a unique tool for measuring not only D₂ receptors (high and low specific activity), but also for measuring the intrasynaptic dopamine tone (high specific activity alone).

- b. Justification and safety information if FDA approved drugs will be administered for non-FDA approved indications or if doses or routes of administration or participant populations are changed.
N/A
- c. Justification and safety information if non-FDA approved drugs without an IND will be administered.
N/A

7. Study Statistics

- a. Primary outcome variables.

Selection of Independent Variables and Primary Outcomes. The primary independent variable in all analyses is the within-subject comparison of SD versus US. We will also evaluate whether sleepiness (SSS), fatigue (diary), positive and negative affect (PANAS-X) and spontaneous pain (diary) are associated with outcomes and include these variables as covariates in secondary analyses when indicated. Primary outcomes were chosen based on evidence from our prior work and the literature, described above. A summary of primary outcomes by aim is presented in Table 2.

Table 2: Summary of Outcome Measures By Aim

AIM	CONSTRUCT	MEASURE
Aim 1-3	1°HA♦ peripheral sensitization 2°HA♦ spinal sensitization	1°HA-Heat pain threshold (°C), treated skin 2°HA-Surface Area (cm ²), mech. HA untreated skin
Aim 2 & 3	Pain Tolerance	Duration (sec) of hand submersion in 4°C Water
Aim 3	Inflammation - Systemic - Cellular - Genomic - Genomic Signaling	Circulating (plasma) IL-6, TNF-α, IL-1RA** Stimulated & Unstim. PBMC levels of IL-6 & TNF PBMC mRNA conc. of IL-6**, TNF-α**, IL-1β** Stimulated & Unstim. PBMC levels of NF-κB

♦ Heat Capsaicin Testing; ** secondary outcomes

- b. Statistical plan including sample size justification and interim data analysis.

Analytic Plan Hypothesis 1.a. (Sleep disruption enhances HA): We will use multilevel longitudinal mixed effects models to test the null hypothesis that baseline and sleep-deprived indices of 1^o & 2^o hyperalgesia are equal. We will also test for differences in linear time trends by condition.

Hypothesis 2.a. (Sleep disruption diminishes morphine analgesia): Similar models will test the null hypothesis of no effect of sleep deprivation on the analgesic effects of morphine on hyperalgesia and cold pain tolerance. We will also test for differences in linear time trends.

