Hypothesis 3.a. (Sleep disruption increases activation of markers of inflammation): We will first compute area-under-the-curve-ground (AUC-G) and -increase (AUC-I) values following standard formulas(134) for the inflammatory markers. AUC allows us to simplify the analysis of the repeated measures data to increase power(134). AUC-G represents the total amount of inflammation during the pre-drug administration segment (blood draws 1-4), whereas AUC-I represents the level of increase in inflammation in response to heat capsaicin (blood draws 3-4), relative to the within-condition baseline levels (blood draws 1 & 2). Mixed effect models will test the difference in marker AUCs between sleep conditions.

Hypothesis 3.b. (Markers of inflammation mediate the effects of sleep disruption on: 1) HA and 2) diminished opioid analgesia): Following the MacArthur approach(135) we will first establish relationships between the markers and both hyperalgesia (HA) and sleep disruption (SD). Thus, these analyses will only be conducted if tests of Hypothesis 3.a. indicate a relationship between SD and activity of a specific marker. For these markers, we will then test the relationship between marker activity and HA using mixed effects models. When significant, interactions between SD and marker activity will be taken as evidence of *mediation* rather than *moderation*, as should a main effect of marker activity after controlling for this interaction and the main effects of SD(135). These analyses use only data from the pre-drug administration segment ;therefore, the placebo and opioid groups are combined. Mixed effects models will test the relationship between marker activity and diminished opioid analgesia, allowing for correlation within individuals across sleep conditions and pre- and post-drug segments. Statistical significance of the main effect of marker activity, the interaction between drug condition and marker activity, or the interaction between drug, marker, and SD will be taken as evidence of a mediating effect of marker activity.

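### Admission order is randomised but no period term is specified, so any first-versus-second-admission effect stays in the error of the Aim 1 and AUC-G sleep contrasts

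*Combined protocol and SAP*

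**What the plan says.** Section 4.a (Randomization Plan) sets up a two-period crossover for sleep inside a parallel drug comparison: "To control for sequence effects, we will counterbalance US and FA conditions by randomizing subjects to 1 of 4 sequences". Each sequence is a drug paired with an order, US first or FA first, and the drug is the same at both admissions. Allocation also uses minimisation "to balance groups on sex, obesity (BMI), and age, since these factors influence pain and inflammation", with Chinese ethnicity as a fourth factor.

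Section 7.a states: "The primary independent variable in all analyses is the within-subject comparison of SD versus US". It names sleepiness, fatigue, affect and spontaneous pain as possible covariates, in secondary analyses only.

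Section 7.b describes the models in prose:
- Hypothesis 1.a uses "multilevel longitudinal mixed effects models to test the null hypothesis that baseline and sleep-deprived indices" of primary and secondary hyperalgesia are equal, plus linear time trends by condition.
- Hypothesis 2.a: "Similar models will test the null hypothesis of no effect of sleep deprivation on the analgesic effects of morphine".
- Hypothesis 3.a: "Mixed effect models will test the difference in marker AUCs between sleep conditions".
- Hypothesis 3.b adds marker activity, drug and their interactions.

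None of these descriptions names admission number, sequence or a minimisation factor. The power section places the linear trends within a sleep condition, so they do not stand in for admission number. The Aim 1 simulation, as described, sets two condition means and no period mean.

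**The concern.** Counterbalancing and adjustment do different work. Counterbalancing lets a period effect cancel from the mean sleep contrast when the two orders are equally represented. It does not take that effect out of the individual FA-US differences, which move up in one order and down in the other. Without a period term, this known spread counts as noise.

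A period effect is plausible here. A subject reaches the second admission having already been through a full day of five sensory-testing sessions, the cold-pressor task with its undisclosed time limit, and the injection. At stake is precision in the Aim 1 contrast, which the plan powers at 80% for an effect of 0.40. If completers end up unevenly split by order, some bias follows as well.

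**Working it through.** **Inputs from the documents.** N = 80 completers from 94 randomised with 15% dropout (94 × 0.85 = 79.9); Aim 1 power of 80% or greater at a standardised effect of 0.40.

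**Assumed, because not given.** The between-condition correlation rho, two-sided alpha of 0.05 for Aim 1, and the period effect pi, in outcome SDs throughout. The calculation uses one summary value per subject and condition, a simplification of the mixed model.

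**Step 1: the plan's own figure.** SD of the paired difference: SD_d = √(2(1 − rho)). Under the normal approximation, power at 0.40 with N = 80 is 71.6% at rho = 0, 80.0% at rho = 0.185 and 94.7% at rho = 0.5. The stated figure cannot be reproduced without rho but fits rho of about 0.2. At rho = 0.2, SD_d = √1.6 = 1.265 and the noncentral t (79 df) gives 79.8%.

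**Step 2: add a period effect with a 40:40 split.** Each FA-US difference has mean tau + pi in one order and tau − pi in the other. Their average is tau, so there is no bias. The unadjusted variance is SD_d² + pi². Noncentrality is 0.40 × √80 / √(1.6 + pi²) = 3.578 / √(1.6 + pi²).

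| pi | Variance | SE ratio | Noncentrality | Power | Equivalent N |
|---|---|---|---|---|---|
| 0 | 1.60 | 1.000 | 2.828 | 79.8% | 80 |
| 0.3 | 1.69 | 1.028 | 2.752 | 77.6% | 75.7 |
| 0.4 | 1.76 | 1.049 | 2.697 | 75.9% | 72.7 |
| 0.6 | 1.96 | 1.107 | 2.556 | 71.4% | 65.3 |

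Equivalent N is 80 × 1.60 / variance. In simulation (SD_d = 1.277, pi from 0 to 0.8) the period-adjusted test keeps about 79% power throughout. The unadjusted test is conservative under balance: at pi = 0.5 its type I error is 3.6%, against 5.0% adjusted.

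**Step 3: unequal completers by order.** Bias = pi × (n1 − n2)/N.
- 43/37: 6/80 = 7.5% of pi.
- 45/35: 10/80 = 12.5% of pi.
- For pi of 0.3 to 0.5, these give 0.075 × 0.3 = 0.02 SD up to 0.125 × 0.5 = 0.06 SD, with type I error of about 4-6%.
- 48/32 with pi = 0.5: 0.20 × 0.5 = 0.10 SD, with type I error of 8.3% unadjusted and 5.2% adjusted.

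**Step 4: which contrasts are exposed.**
- Aim 1: exposed. Table 2 defines the outcomes as levels (threshold in °C, area in cm²), so nothing within the admission removes a shift.
- AUC-G: exposed, because it measures the total level.
- AUC-I: an additive shift cancels, because it is taken relative to baseline draws in the same condition.
- Aim 2: the power section uses four processes, one per segment and sleep condition. Read as (post − pre) × (FA − US) × drug, an additive shift cancels within each admission. A period effect on the drug response would not. Hypothesis 2.a does not itself state this contrast, so it should be confirmed.

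**The case against.** The strongest reply is that the design already limits period effects. Screening visit 2 familiarises every subject with heat, capsaicin and pain testing; visit 3 gives an adaptation night; washout is at least two weeks; and skin sites are counterbalanced across admissions. This makes a large effect less likely. It does not rule one out, because screening includes no injection and no full testing day, and the cited test-retest stability concerns four rekindlings, not separate admissions.

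The power loss may also be harmless. At rho = 0.5, power at 0.40 with pi = 0.6 is still 86%. At the pilot effect of 0.57, with rho = 0.2 and pi = 0.6, it is 95%. Both figures stand.

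A reader might go further in four ways that the documents do not support:
- That every within-subject test loses precision. AUC-I and the pre/post reading of Aim 2 are protected from an additive shift.
- That dropout will cause bias. Nothing suggests that it differs by order. In Aim 2, an order imbalance shared by both drug groups cancels from the between-drug contrast.
- That omitting the minimisation factors adds error to the sleep contrast. They are subject-level, so their main effects cancel in complete pairs. A sequence term likewise recovers no within-subject precision.
- That the plan excludes these terms. Section 7.b is narrative and silent on them.

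**Conclusion.** The point holds for the Aim 1 and AUC-G contrasts: order is randomised, no period term is specified, and the described models would leave any period effect in the error. The Aim 1 cost is about 2 power points for a period effect of 0.3 outcome SD and about 8 for 0.6, assuming rho of 0.2 and two-sided alpha of 0.05. A higher correlation, or a true effect near the pilot value, leaves ample power. Under balanced order the consequence is lost precision, not false positives. Bias needs unequal completers by order and is small for modest imbalances. This does not threaten the trial's validity. It is a nearly free improvement that is best fixed before the data are seen, since silence leaves the choice open until then.

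**What to change.** Add to section 7.b:
- Admission number (first or second) as a fixed effect in the models for Hypotheses 1.a, 3.a and the sleep-contrast part of 3.b.
- In 2.a, admission number plus its interaction with the drug response, with a statement that the test is the pre/post by sleep by drug contrast if that is intended.
- Sex, age, BMI and Chinese ethnicity as fixed effects in models with a between-drug comparison (2.a and the drug part of 3.b), because allocation is minimised on them.

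A sequence term is optional. All the variables are already recorded. The cost is a short addition to the text and a few degrees of freedom out of 80 completers, with no change to design, visits or sample size.
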